## Subject Protection

Data will be securely stored on Qualia Life Sciences servers, accessible only to authorized personnel. Data analysis will be performed after the completion of the data collection period. Direct participant identifiers (such as name, contact information, etc.) will be replaced by a 10-digit code during data analysis, with the code key linking the data set to individually identifiable information stored separately.

---

## Compensation

Participants will receive up to \$300 in Qualia Life Sciences store credit: \$125 for baseline blood test, \$125 for end-of-intervention blood test, and a \$50 bonus upon full completion.

---

## Risk And Benefits

The potential risks and benefits of participating in this study will be fully explained to participants in their informed consent documentation. Risks include potential side effects from the product—nausea, diarrhea, bloating, headache, dizziness, increased anxiety, mood changes, itching, sexual dysfunction, and the possibility of drug-drug interactions—as well as the possibility of no improvement in blood Vitamin C levels or symptoms assessed by PROMIS Cognitive Function - Short Form 8a, the Perceived Stress Scale-10 measures, and Single-item

Assessment of Immune Fitness. Benefits include the potential for increased blood vitamin C levels, decreased oxidative stress, supporting the body's natural immune responses, and improvement in quality of life.

No adverse effects in human trial studies have been reported in the reviewed literature regarding the ingredients in the active product at the doses used in this study. It is extremely unlikely that participants will experience health complications due to dosage amount. If any adverse events occur, [name], ND, will assess the appropriate treatment and action (e.g., seek medical treatment). Qualia Life Sciences is not able to offer financial compensation should a participant be injured as a result of participating in this research. However, participants are not precluded from seeking to collect compensation for injury related to malpractice, fault, or blame on the part of those involved in the research. This information is included in the consent form.

---

## Statistical Methodology

Data will be assessed for normality using the Shapiro-Wilk test and by evaluating skewness and kurtosis. Descriptive statistics will be reported as mean (SD) for continuous variables and frequencies (percentages) for categorical variables. For each outcome, changes from baseline will be computed at subsequent time points, and paired t-tests or linear mixed-effects models will be used to evaluate within-group differences. Between-group comparisons will be conducted using linear mixed-effects models with fixed effects for group, time, and their interaction, and a random intercept for participants to account for repeated measures. Data that do not meet the assumptions of normality will be analyzed using appropriate non-parametric statistical tests. Estimated coefficients, 95% confidence intervals, and p-values for interaction terms will be extracted at each time point. Moderator variables will be considered in adjusted models. Analyses will be performed using Python (statsmodels). The sample size was estimated to yield 80% power to detect an effect size (Cohen's  $d = 0.80$ ) with a two-tailed t-test at a 0.05 significance level.

---

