## SUMMARY

This is a randomized, double-blind, placebo-controlled, parallel-group, study evaluating the effect of a Qualia Vitamin C+ formulation on Whole Blood Vitamin C levels in the blood of healthy adults aged 25 years or older. Approximately 36 participants will be randomized to one of two study arms: Qualia Vitamin C+ or placebo. Each participant will take two capsules of their assigned product once daily in the morning, with or without food, over a 28-day period. The primary outcome is the change in blood vitamin C levels, assessed via in lab blood collection at baseline and study completion. Secondary endpoints include questionnaires measuring health-related cognitive functioning and stress (PROMIS Cognitive Function - Short Form 8a and the Perceived Stress Scale-10), the Single-item Assessment of Immune Fitness, evaluation of safety and tolerability, and an Overall Experience Questionnaire (Appendices 1, 4-7). All assessments, including electronic questionnaires, are completed remotely without in-person visits.

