## OUTCOMES

### Primary Objective

To assess between-group differences in the change in blood Vitamin C levels from baseline to Day 28 following supplementation with Qualia Vitamin C+ versus placebo.

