## Study Schedule

Days 1-28 are when participants will take the test formulas or placebo.

Screening (prior to enrollment (Day -21 to -15): Complete online prescreen questionnaire and provide electronic informed consent.

Baseline Assessments (Day -14 to -7):

1. Conduct Ulta Labs Vitamin C Test
2. Complete PROMIS Cognitive Function - Short Form 8a
3. Complete Perceived Stress Scale-10
4. Complete Single-item Assessment of Immune Fitness
5. Complete Safety and Tolerability survey

Note: Successful completion of baseline assessments and conformation of lab draw are required to ship a participant the study product.

Day 7 Assessments: Complete Safety and Tolerability survey.

Day 14 Assessments:

1. Complete PROMIS Cognitive Function - Short Form 8a
2. Complete Perceived Stress Scale-10
3. Complete Single-item Assessment of Immune Fitness
4. Complete Safety and Tolerability survey

Day 21 Assessments: Complete Safety and Tolerability survey.

Day 29 Assessments:

1. Conduct Ulta Labs Vitamin C Test
2. Complete PROMIS Cognitive Function - Short Form 8a
3. Complete Perceived Stress Scale-10
4. Complete Single-item Assessment of Immune Fitness

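### The planned between-group test of vitamin C does not adjust for baseline; adjusting would usually gain precision for one degree of freedom

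*Combined protocol and SAP*

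**What the plan says.** The Primary Objective is "To assess between-group differences in the change in blood Vitamin C levels from baseline to Day 28". The Summary has the outcome "assessed via in lab blood collection at baseline and study completion", and the Study Schedule lists "Conduct Ulta Labs Vitamin C Test" at baseline (Day -14 to -7) and at Day 29 only. Each participant therefore has two vitamin C values.

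Under Statistical Methodology, the sentence containing "changes from baseline will be computed at subsequent time points" continues into within-group testing. The next sentence governs the comparison between arms: "linear mixed-effects models with fixed effects for group, time, and their interaction, and a random intercept for participants". Inference is on the interaction: "Estimated coefficients, 95% confidence intervals, and p-values for interaction terms will be extracted at each time point". The only mention of adjustment is "Moderator variables will be considered in adjusted models", which names no variable. The sample size is justified "with a two-tailed t-test at a 0.05 significance level" with Cohen's d = 0.80 and 80% power. Number of Participants gives about 36 in total, 18 per arm.

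**The concern.** A mixed model can look as though it already deals with baseline. Here it does not. The model treats baseline as one of two outcomes, and its group main effect lets the arms have different baseline means. With two visits, the interaction subtracts the full baseline difference between arms from the Day 29 difference, whatever the actual relation between the two measurements.

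Precision is at stake. Stratification is by gender and age, so nothing in the design balances baseline vitamin C. At 18 per arm, chance differences in mean baseline are not small. The trial already collects the value that would absorb them, and on its own inputs it has no spare power.

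**Working it through.** **Inputs.** From the documents: 18 per arm, two-sided alpha 0.05, d = 0.80, two vitamin C measurements. Not in the documents, so assumed: the correlation r (0.3 to 0.9), the ratio k of the Day 29 SD to the baseline SD (first k = 1), and d expressed in SDs of change.

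**1. The plan's own figure.** By the normal approximation, n per arm = 2(1.960 + 0.842)²/0.80² = 24.5, so 25; the t-test needs 26. At 18 per arm the noncentrality is 0.80/√(2/18) = 2.40 on 34 df, which gives 64.5% power. The stated 80% is not reproduced. The starting point below is 64.5%.

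**2. What the planned model tests.** The specified model was fitted to one simulated complete data set (18 per arm, two visits). The interaction was 0.9109 (SE 0.2623). The plain difference in mean change was 0.9109 (SE 0.2623), the same. A baseline-adjusted model on those data had SE 0.2006.

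**3. Variance ratio, equal SDs.** Let s be the SD at each visit.
- Variance of change: 2s²(1 − r)
- Residual variance after baseline adjustment: s²(1 − r²)
- Ratio, adjusted to unadjusted: (1 − r²)/[2(1 − r)] = (1 + r)/2
- Small-sample cost of estimating the slope: 1 + 1/(N − 4) = 33/32 for N = 36, with 33 error df

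**4. Power at 18 per arm.** Adjusted noncentrality = 2.40/√(ratio × 33/32).

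| r | (1 + r)/2 | × 33/32 | Noncentrality | Adjusted power | Simulated power, unadjusted / adjusted | Per arm for 80%, adjusted |
|---|---|---|---|---|---|---|
| 0.3 | 0.65 | 0.670 | 2.93 | 81.2% | 64.4% / 80.8% | 18 |
| 0.5 | 0.75 | 0.773 | 2.73 | 75.5% | 64.5% / 75.6% | 20 |
| 0.7 | 0.85 | 0.877 | 2.56 | 70.1% | 64.3% / 70.0% | 23 |
| 0.9 | 0.95 | 0.980 | 2.42 | 65.3% | 64.6% / 65.6% | 25 |

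The simulated columns rest on 20,000 trials per r. At r = 0.95 the factor is 0.975 × 33/32 = 1.005, so the gain is gone.

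**5. Unequal SDs.** The general large-sample ratio is k²(1 − r²)/(1 + k² − 2rk), and the slope on baseline is rk. The ratio reaches 1 when the slope is 1.
- r = 0.7, k = 1.5 (slope 1.05): 1.1475/1.15 = 0.998, no gain
- r = 0.5, k = 1.5 (slope 0.75): 1.6875/1.75 = 0.96, against 0.75 with equal SDs
- r = 0.5, k = 0.75 (slope 0.375): 0.4219/0.8125 = 0.52, a larger gain

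**6. Scale of d.** The plan does not say which SD standardizes d. If it is the SD of a single measurement, with k = 1, power goes from 50.4% to 67.2% (r = 0.3), 64.5% to 75.5% (r = 0.5) and 85.3% to 89.5% (r = 0.7).

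**7. Chance imbalance.** The SD of the between-arm difference in mean baseline is √(2/18) = 0.33 baseline SDs. At r = 0.5 and k = 1, an imbalance of that size moves the change-score estimate by (1 − 0.5) × 0.33 = 0.17 baseline SDs. The SD of change is then √(2 × 0.5) = 1 baseline SD, so the shift is 0.17 SDs of change, about a fifth of d = 0.80.

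**The case against.** The strongest defence is that nothing here is wrong. A change-score comparison is unbiased in a randomized trial and answers the Primary Objective as worded. That stands. A reader might infer from the imbalance calculation that the planned estimate is biased. It is not: averaged over randomizations the imbalance is variance, and the ratio in step 3 already counts it.

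Three other strong readings also fail. First, that change scores over-correct whenever r is below 1: the condition is that the slope rk is below 1, and the documents give neither r nor k. Second, that the mixed model would be fitted to computed changes, leaving one row per person and no estimable interaction: the sentence on computing changes belongs to the within-group tests, and the plan does not clearly propose such a model. Third, that a usable baseline is guaranteed for everyone: the Study Schedule requires confirmation of the lab draw before product is shipped, which is close to that but is not a usable result.

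The sponsor might reply that the sentence on moderator variables covers baseline. It leaves room for it, but it commits the primary analysis to nothing and leaves the choice of covariate open until the data are seen.

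It is also fair to say that the size of the gain is unknown. At r = 0.9 it is under one percentage point.

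**Conclusion.** The point holds as a low-cost improvement, not as an error in the plan. The planned interaction test for vitamin C is, on complete data, the unadjusted difference in mean change, and no text commits to adjusting it for baseline. With equal SDs and d in SDs of change, adjustment raises power at 18 per arm from 64.5% to between 81.2% (r = 0.3) and 65.3% (r = 0.9). The gain is smaller or absent if r is very high or if greater Day 29 variability brings the baseline slope near 1, and larger if Day 29 variability is lower. All of these figures depend on r, k and the scale of d, which the documents do not supply.

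A reader might also infer that adjustment rescues the sample-size claim. On these assumptions it reaches 80% at 36 participants only if r is about 0.3 or lower, so the power statement needs its own correction.

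**What to change.** Prespecify, before unblinding:
- **Primary analysis.** A linear model of Day 29 vitamin C on treatment with baseline vitamin C as covariate, reporting the adjusted mean difference with a t-based 95% confidence interval. The treatment coefficient is identical if change is the outcome, so the Primary Objective is preserved.
- **Sensitivity analysis.** The unadjusted comparison of change.
- **Questionnaires (baseline, Day 14, Day 29).** Keep the mixed model, so that partial data and repeated measures are still used, and adjust for that questionnaire's own baseline. Either enter baseline as a covariate with Days 14 and 29 as outcomes, or constrain the arms to a common baseline mean.
- **Wording.** Name the covariates in place of the open reference to moderator variables, and say how the non-parametric fallback relates to the adjusted primary model, since as written it could displace it.

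The cost is SAP text and one degree of freedom for the primary model. No new data are needed.

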# NUMBER OF PARTICIPANTS

Number of Participants: Approximately 36 total (18 in each arm)

---

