## Randomization And Blinding

Participants will be randomized in a 1:1 ratio to one of two study groups: Qualia Vitamin C+ or placebo. To maintain double-blinding, a designated Qualia Life Sciences staff member independent of the research team will assign and label all study products as A or B. Both participants and study personnel will remain blinded to group assignments until study completion. Unblinding will occur only after all study data have been collected and finalized.

---

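### The random-intercept model in statsmodels, with no small-sample degrees of freedom, runs at 5.8% rather than 5% for vitamin C, and its Day 29 questionnaire tests run higher if correlation falls with time

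*Combined protocol and SAP*

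**What the plan says.** The Statistical Methodology section sets between-group comparisons as "linear mixed-effects models with fixed effects for group, time, and their interaction, and a random intercept for participants". It then states that "Estimated coefficients, 95% confidence intervals, and p-values for interaction terms will be extracted at each time point", so time is read as categorical and each follow-up visit has its own group-by-time term. On software: "Analyses will be performed using Python (statsmodels"). The section names no small-sample degrees-of-freedom method, residual covariance structure, random slope or robust variance.

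The sample-size sentence in the same section is framed "with a two-tailed t-test at a 0.05 significance level", so the design basis is a t reference at 5%. The Number of Participants section gives "Number of Participants: Approximately 36 total (18 in each arm").

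Under Study Schedule, vitamin C is measured twice (baseline and Day 29). PROMIS Cognitive Function, PSS-10 and the immune fitness item are collected three times (baseline at Day -14 to -7, Day 14 and Day 29).

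**The concern.** There are two separate causes.

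1. **Reference distribution (all outcomes).** MixedLM in statsmodels reports Wald z-tests and intervals of plus or minus 1.96 standard errors by default. With 36 participants the correct reference is a t distribution with few degrees of freedom.
2. **Covariance (questionnaires only).** A random intercept alone makes every pair of visits equally correlated. Baseline to Day 29 spans 36 to 43 days (29 + 7 and 29 + 14), while Day 14 to Day 29 spans 15. The PROMIS and PSS-10 forms in the appendices ask about the past week and the immune item about the present moment, so some decay in correlation is plausible. If it occurs, the pooled residual variance is too small for the baseline-to-Day 29 change.

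At stake are the stated 5% level and 95% intervals: slightly for the primary outcome, and possibly by more for end-of-treatment results on cognition, stress and immune fitness. The section on intended use of study data allows aggregated outcomes to support publications and marketing.

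**Working it through.** **Inputs.** From the documents: 18 per arm, two-sided 0.05, two vitamin C visits, three questionnaire visits, random intercept only, statsmodels. Assumed: complete data, normal outcomes, equal variances at each visit (except in the random-slope runs), and the between-visit correlations, which the documents do not give.

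**The plan's own figures.** A two-tailed t-test on change with 18 per arm has 36 - 2 = 34 degrees of freedom and critical value 2.032, which gives exactly 5%. (The stated 80% power at d = 0.80 does not reproduce: power at 18 per arm is 64.5%. That is a separate matter and does not affect the error rates below.)

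**Vitamin C.** With two balanced visits the random-intercept REML interaction statistic equals the two-sample t statistic on change. Six MixedLM fits agreed with the t-test to about four decimals and used a half-width of 1.96 standard errors.

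- Error rate: P(|t34| > 1.96) = 5.82%, so coverage is 94.2%.
- Interval width: 1.960 / 2.032 = 0.964, about 3.6% too narrow.
- With an assumed 15 per arm (28 degrees of freedom): 6.00%.

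No correlation is assumed here, because one pair of visits has only one correlation.

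**Questionnaires, analytic check.** With unit variances the random-intercept model takes the variance of every change score as 2(1 - mean r). The true value for one pair of visits is 2(1 - r for that pair). Take correlations 0.7 (baseline-Day 14), 0.5 (baseline-Day 29) and 0.7 (Day 14-Day 29):

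- Mean r = 1.9/3 = 0.633, so the model variance is 2 × 0.367 = 0.733.
- Day 29: true variance 2 × 0.5 = 1.0. Model SE / true SE = √0.733 = 0.856, about 14% too small. The large-sample error is P(|Z| > 1.96 × 0.856) = 9.3%.
- Day 14: true variance 2 × 0.3 = 0.6. SE ratio = √(0.733/0.6) = 1.106, about 11% too large. The large-sample error is P(|Z| > 1.96 × 1.106) = 3.0%.

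**Questionnaires, simulation under the null (18 per arm, z reference).** Triplets are in the order baseline-Day 14, baseline-Day 29, Day 14-Day 29. Where independent runs differ, the range is shown.

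| Assumed correlation | Day 29 error | Day 14 error |
|---|---|---|
| Equal (0.3 to 0.9) | 5.4-5.5% | 5.4% |
| Mild decay (.65, .6, .7) | 7.0-7.2% | 5.5% |
| (.7, .5, .7) | 9.7-10.3% | 3.3-3.4% |
| (.6, .5, .8) | 9.9-10.1% | 6.3-6.7% |
| AR(1) by visit, 0.3 to 0.9 | 7.6-11.0% | 3.0-4.4% |
| AR(1) on actual days, 0.5 to 0.9 per 14 days | 8.3-10.8% | 4.9-5.5% |
| Random slopes, slope variance 0.1 to 2 times residual variance | 6.5-13.4% | 2.0-4.9% |

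Direct MixedLM fits at AR(1) 0.7 gave 10.1% at Day 29 and 3.5% at Day 14.

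**Separating the causes.** The pooled three-visit residual has 2 × 34 = 68 degrees of freedom, and P(|t68| > 1.96) = 5.4%, so the z reference adds about 0.4 points. A t reference with 68 degrees of freedom still leaves 9.4% at Day 29 under AR(1) 0.7. The rest comes from the covariance. A t-test on Day 29 change held 4.9-5.1% in the triplet scenarios.

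**The case against.** The case on the other side is substantial, and several parts stand.

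- **A reader might infer that the questionnaires have a 10% error rate, or that 10% is the ceiling.** The documents support neither. They give no correlations. The rate is about 5.5% if correlations are equal and can pass 13% with strong random slopes, so 10% is one illustrative value.
- **A reader might infer that every p-value and interval is too optimistic.** That holds for vitamin C and for the Day 29 terms in the scenarios examined. The plan also extracts Day 14 terms, and these are conservative in several decay scenarios.
- **A reader might infer that the primary outcome shares the covariance problem.** It does not. With two visits a random intercept imposes no wrong pattern. The vitamin C excess is 0.8 points, and a stated t reference with 34 degrees of freedom cures it.
- **The intended marketing use might suggest that the error favours the product.** The inflation is two-sided: of about 10% at Day 29, about half would favour the product, against a nominal 2.5%. The intended-use section does not single out these secondary outcomes.
- The plan sends non-normal data to non-parametric tests. The 0-10 immune item and the bounded PROMIS scores may take that route, where these rates do not apply.
- The plan names the software but does not say that its default reference will be used. An analyst could apply a t reference by hand, but nothing in the text requires it.

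These points limit the size and reach of the concern. They leave the gap: neither the degrees of freedom nor the covariance is specified in a way that protects the stated level.

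**Conclusion.** The concern holds in limited form. For vitamin C the planned test, with the software's default reference, runs at 5.8% instead of 5%, and its interval is about 3.6% too narrow. This follows from 18 per arm and two visits, given complete and normal data. It is a small fault, but it falls on the primary outcome.

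For the questionnaires the mechanism is sound and the size is conditional. The Day 29 error exceeded 5% in every scenario examined, but by half a point or less under equal correlation. A material excess needs correlation to decay with time. The visit spacing makes that plausible, and the documents do not establish it. No single direction can be claimed for Day 14. The plan should be changed before unblinding, because the cure is inexpensive and needs no new data.

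**What to change.** For between-group tests, replace the random-intercept model with ordinary least squares ANCOVA of the follow-up value on group and baseline. Fit it separately at Day 29 (all outcomes) and at Day 14 (questionnaires), and take t-based p-values and 95% intervals from statsmodels OLS. ANCOVA with t inference held 4.7-5.0% in simulation.

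If a repeated-measures model is kept for the questionnaires, specify an unstructured covariance with Kenward-Roger or Satterthwaite degrees of freedom. This may need software other than the one named.

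**Cost.** SAP wording and simpler code; no added participants, visits or data.

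- *Vitamin C precision:* usually a gain. At a baseline correlation of 0.6 the mean 95% half-width is 0.547 SD with ANCOVA and 0.580 SD as planned (0.547/0.580 = 0.94, about 6% narrower). It is narrower at correlations up to about 0.7, about equal at 0.8 and slightly wider at 0.9.
- *Day 29 questionnaires:* intervals widen if correlation decays (0.592 against 0.557 SD in the decaying cases).
- *Missing data:* per-visit ANCOVA drops from the Day 29 analysis anyone with Day 14 but no Day 29 questionnaires, whereas a three-visit model would use them. If such losses are expected, this is the main reason to prefer the unstructured model for the questionnaires.

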**At this moment, I rate my immune fitness as follows:**

0	1	2	3	4	5	6	7	8	9	10
----------	----------	----------	----------	----------	----------	----------	----------	----------	----------	-----------

Very poor
Excellent

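### A normality check without cut-offs can replace the planned primary model with an unnamed non-parametric test, and the promised estimate and confidence interval are then lost

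*Combined protocol and SAP*

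**What the plan says.** All of the relevant text is in the Statistical Methodology section.

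- The check: "Data will be assessed for normality using the Shapiro-Wilk test and by evaluating skewness and kurtosis". There is no significance level for the test, no limit for skewness or kurtosis, and no rule for when the three disagree. The section does not say whether raw values, changes, each arm separately or model residuals are examined.
- The planned model: "Between-group comparisons will be conducted using linear mixed-effects models with fixed effects for group, time, and their interaction", with a random participant intercept.
- The switch: "Data that do not meet the assumptions of normality will be analyzed using appropriate non-parametric statistical tests". No test is named.
- The promised output, in the very next sentence: "Estimated coefficients, 95% confidence intervals, and p-values for interaction terms will be extracted at each time point".

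The Primary Objective is "To assess between-group differences in the change in blood Vitamin C levels from baseline to Day 28". The switch applies to every outcome and does not exempt this one. The plan never labels a primary analysis. That the mixed model is primary follows from its being the only named method for between-group comparisons. No other section supplies the missing test, threshold or replacement estimate.

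**The concern.** Two adjacent sentences do not fit together. One sends non-normal data to a non-parametric test. The other promises interaction coefficients with confidence intervals, which a rank test does not give. If the check fails for vitamin C, following the plan means losing its stated primary result.

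The decision is also taken after the outcome data are in hand, by criteria that leave room for judgement. Two careful analysts could read the rule differently, choose different methods and report different conclusions. In a trial of about 36 people whose results may support publications and marketing (Intended Use of Study Data), the primary method should not be open in this way.

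**Working it through.** **The plan's own figure.** The sample size is justified by 80% power for d = 0.80 with a two-tailed t-test at 0.05. By the normal approximation, n per arm = 2(1.96 + 0.84)²/0.80² = 24.5, so 25; the exact t calculation gives 26. At the planned 18 per arm, t-test power is 64.5%. The stated figure is therefore not reproduced. That is a separate matter and nothing below depends on it.

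**What is lost at a switch.** The Study Schedule has vitamin C measured only at baseline and Day 29. With two time points and complete data, the interaction coefficient is

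(mean Day 29 − mean baseline, active) − (mean Day 29 − mean baseline, placebo),

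that is, the difference in mean change, and its test is equivalent to a t-test on change. A Mann-Whitney test on change gives a p-value for a different contrast. It does not give this coefficient or its interval.

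**How often the switch occurs.** From the documents: 18 per arm, 1:1. Assumed, because the documents give no values: log-normal vitamin C with log SD 0.3 to 0.5, baseline to follow-up correlation r of 0.3 to 0.5, Shapiro-Wilk at 0.05 on pooled change, and Mann-Whitney on change as the fallback. The switch occurs in about 14 to 44% of simulated trials, counting runs with no effect and runs with a 0.8 SD shift on the log scale.

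**Whether it changes the conclusion.** At the 0.8 SD shift, the t-test and Mann-Whitney test on change fall on opposite sides of 0.05 in about 8 to 11% of trials. A second set of simulations generated the changes directly as normal, t with 5 df, or log-normal with sigma 0.25, 0.5 or 0.8 (10,000 trials per scenario). There the disagreement at d = 0.80 was 7 to 21%. Two reasonable readings of the check (either arm fails, or the model residuals fail) chose different methods in 3 to 15% of trials.

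**Whether it costs power.** The switch has to be compared with the same change-score contrast without it (3,000 trials per row, 0.8 SD shift):

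| log SD | r | With switch | Without switch | Difference (points) |
|---|---|---|---|---|
| 0.3 | 0.3 | 52.9% | 53.5% | −0.6 |
| 0.3 | 0.5 | 66.0% | 66.8% | −0.8 |
| 0.5 | 0.3 | 51.8% | 51.9% | −0.1 |
| 0.5 | 0.5 | 65.0% | 64.9% | +0.1 |

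The simulation standard error of a single entry is about √(0.53 × 0.47/3000) = 0.9 points.

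**Whether it inflates type I error.** In the log-normal-level simulations, error with the switch was 4.3 to 5.3%. In the second set, a switch rule fixed in advance gave 4.7 to 5.6%, choosing the smaller p-value gave 5.8 to 6.5%, and the t-test on change with no switch gave 4.3 to 5.1%. The switch therefore protects against little.

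**The case against.** The strongest reply is that testing normality and falling back to ranks is common practice and does little measurable harm here. On error rates and power that is right: type I error stays close to 5%, and power moves by less than 1 point.

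A reader might infer more than the documents support in four ways.

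- **That precision is lost at the switch.** It is not. Power with and without the switch is nearly equal. Log-scale ANCOVA reaches about 66 to 75% in simulation, but that gain comes mainly from baseline adjustment. It is also flattered by data generated on the log scale.
- **That rank tests discard a baseline adjustment.** The plan has no baseline covariate. A rank test on change uses baseline just as the planned contrast does.
- **That raw, pooled data are tested.** The text says only that data are assessed. The defect is that the tested quantity is not stated.
- **That the check will nearly always fail.** Rates of 53 to 98% come from raw values of the 0 to 10 immune fitness item ("At this moment, I rate my immune fitness as follows") under assumed distributions. That is a secondary outcome, so these rates say nothing about vitamin C, whose distribution the documents do not describe.

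A Hodges-Lehmann shift with an interval could accompany a rank test. The plan does not name it, and it estimates a different quantity from the promised coefficient.

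What remains untouched is that the method is not fixed and the promised estimate can disappear.

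**Conclusion.** The point holds as a defect of specification with a real consequence. The plan lets an undefined check replace its primary between-group model with an undefined test, and the result is then reported without the coefficient and interval the plan promises. It should be corrected before unblinding.

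The text alone establishes the conflict. Its frequency (about 14 to 44% of trials) and the chance that the two tests disagree (about 8 to 11%) rest on the assumed log-normal shape, correlations, Shapiro-Wilk level and Mann-Whitney fallback. They are indications of scale and do not predict this trial. The documents do not support a claim of lost power or of material type I error inflation.

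**What to change.** Delete the sentence that switches methods, and state one primary analysis to be reported whatever the normality result: ANCOVA of Day 29 vitamin C on group, baseline vitamin C, gender and age, giving the adjusted mean difference with its 95% confidence interval. Gender and age belong there because randomization is stratified by both. With baseline in the model, the adjusted difference at Day 29 is also the adjusted difference in change, so the primary objective is kept. Examine residuals descriptively only.

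Name one sensitivity analysis, for example rank ANCOVA, a permutation p-value or log-scale ANCOVA. Report it beside the primary result, never in its place. A log-scale primary analysis would turn the estimate into a ratio, so it is better used as the sensitivity analysis. Use the same untransformed, baseline-adjusted approach for the questionnaires.

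A separate benefit comes from the baseline adjustment, not from removing the switch. In simulation, power rises from about 51 to 66% for the change-score contrast to about 60 to 73%, for assumed correlations of 0.3 to 0.5.

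The cost is SAP wording: no added participants, visits or assays. The one drawback is slightly more reliance on the linear model if residuals are skewed, which the named sensitivity analysis covers.
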